In designing and manufacturing new drugs, two new and strong trends have emerged. Biotechnology has developed a new group of biological drugs, and offers a completely new approach to drug design. And there is a growing trend towards the use of herbal products in the treatment of diseases (Robert,2000). The use of medicinal plants for the treatment of diseases has been around for centuries, and is still considered a major treatment in many developed and developing countries (Sindambiwe,1999). Currently, most modern drugs are chemical. But at the same time, about 30% of pharmaceutical products are of plant origin (Robert,2000). New research has shown that some herbs are used in traditional medicine. They have antiviral effects. The extract of some plants has been described as an antiviral agent (Vanden,1986). In particular, the antiviral effects of several types of flavonoids (Hayashi,1992 & 1997), Anthraquinones and their derivatives have been studied (Andersen, 1991 & Sydiskis, 1991). Hypericin and Pseudohypericin Which have a significant effect on retroviruses. From plant species Hypericum are taken (Meruelo,1988). It has also been shown that entroquinones that inhibit polyphenolic or sulfonate bridges inhibit the reverse transcriptase enzyme (Schinazi, 1990). Treatment of viral infections with existing drugs for reasons such as drug resistance due to mutations in viruses. Some latent infections and recurrent infections sometimes fail. Therefore, there is a growing need to find new antiviral compounds (Field,1994). Research on medicinal plants and their compounds is a useful strategy in this regard (Vlietinck, 1991). In the present study, the effects of inhibiting the antiviral activity of a herbal drug consisting of several plant species on the clinical status of 35 positive corona patients were investigated.

Related studies

The coronavirus disease 2019 (COVID-19) pandemic has caused a worldwide outbreak of respiratory illness. This review aims to evaluate the effectiveness and adverse events of herbal medicines for the treatment of COVID-19. METHODS: Twelve databases were searched through 12 May 2020. Randomized controlled trials (RCTs) and quasi-RCTs

assessing the effects of herbal medicines for the treatment of COVID-19 were eligible. The study selection and data extraction were performed by two independent reviewers. The Cochrane risk of bias tool was used for the assessment of the risk of bias in all included RCTs. Mean differences (MDs), risk ratios (RRs) and odds ratios (ORs) with 95% confidence intervals (CIs) were calculated, and the effect sizes of the studies were pooled. RESULTS: Seven RCTs with a total of 855 patients were included. All included trials compared the combined therapy of herbal medicine with Western medicine to Western medicine alone. The combined therapy significantly improved the total effective rate (RR 1.23, 95% CI 1.13 to 1.34, $p < 0.001$), cough symptom disappearance rate (RR 1.45, 95% CI 1.12 to 1.89, $p = 0.005$), and sputum production symptom disappearance rate (RR 1.73, 95% CI 1.19 to 2.50, $p = 0.004$). Beneficial effects of the combined therapy were also seen in TCM syndrome score of cough (MD -1.18, 95% CI -1.34 to -1.03, $p < 0.001$), fever (MD -0.62, 95% CI -0.79 to -0.45, $p < 0.001$), dry and sore throat (MD -0.83, 95% CI -1.45 to -0.20, $p = 0.009$), and fatigue (MD -0.60, 95% CI -1.04 to -0.17, $p = 0.007$). The overall risk of bias of the included studies was unclear. No serious adverse events were reported. CONCLUSION: Significant effects of the combined therapy of herbal medicine with Western medicine were found, and revealed the potential role of herbal medicine in treating COVID-19. More high-quality RCTs are needed to further validate the effectiveness and adverse events of herbal medicine in the treatment of COVID-19. (Ang, L., et al, 2020).

Coronavirus disease-2019 (COVID-19) pandemic caused by the severe acute respiratory syndrome coronavirus-2 (SARS-CoV-2) is evolving across the world and new treatments are urgently needed as with vaccines to prevent the illness and stem the contagion. The virus affects not only the lungs but also other tissues, thus lending support to the idea that COVID-19 is a systemic disease. The current vaccine and treatment development strategies ought to consider such systems medicine perspectives rather than a narrower focus on the lung infection only. COVID-19 is associated with elevated levels of the inflammatory cytokines such as interleukin-6 (IL-6), IL-10, and interferon-gamma (IFN-gamma). Elevated levels of cytokines and the cytokine storm have been linked to

fatal disease. This suggests new therapeutic strategies through blocking the cytokine storm. IL-6 is one of the major cytokines associated with the cytokine storm. IL-6 is also known to display pleiotropic/diverse pathophysiological effects. We suggest the blockage of IL-6 signaling and its downstream mediators such as Janus kinases (JAKs), and signal transducer and activators of transcription (STATs) offer potential hope for the treatment of severe cases of COVID-19. Thus, repurposing of already approved IL-6-JAK-STAT signaling inhibitors as well as other anti-inflammatory drugs, including dexamethasone, is under development for severe COVID-19 cases. We conclude this expert review by highlighting the potential role of precision herbal medicines, for example, the Cannabis sativa, provided that omics technologies can be utilized to build a robust scientific evidence base on their clinical safety and efficacy. Precision herbal medicine buttressed by omics systems science would also help identify new molecular targets for drug discovery against COVID-19. (Dzobo, K., et al, 2021).

Coronavirus disease 2019 (COVID-19) is a novel, human-infecting beta-coronavirus enveloped, positive-sense single-stranded RNA viruses, similar to the severe acute respiratory syndrome (SARS) infection that emerged in November 2002. In traditional Chinese medicine (TCM), the epidemic disease concepts of "febrile epidemics" (wenyi) or "warm diseases" (wenbing) are based on geographic and cultural aspects, and Chinese herbal medicine (CHM) played an important role in the treatment of epidemic diseases. CHM was widely used to treat patients suffered with SARS almost two decades ago during outbreak of SARS, with proven safety and potential benefits. TCM has also been widely used to treat cancer patients for a long history and much of them associate with immunomodulatory activity and are used to treat coronavirus-related diseases. We propose the use of CHM treatment principles for clinical practice, based on four main stages of COVID-19 infection: early, intermediate, severe, and convalescence. We suggest corresponding decoctions that exhibit antiviral activity and anti-inflammatory effects in the early stage of infection; preventing the disease from progressing from an intermediate to severe stage of infection; restoring normal lung function and improving consciousness in the severe stage; and ameliorating pulmonary and vascular injury in

the convalescent stage. We summarize the pharmaceutical mechanisms of CHM for treating coronavirus via antiviral, anti-inflammatory and immunomodulatory effects. (Huang, S. T., et al, 2020).

Background: There is currently no effective treatment against coronavirus disease 2019 (COVID-19). The optimal selection of interventions targeting the virus is unknown. Therefore, evidence from randomized controlled trials (RCTs) to support specific treatment against COVID-19 is urgently needed. The use of Chinese herbal medicines (CHMs) might have a role in the treatment and symptomatic management of patients with COVID-19. It was aimed at providing an overview of the available evidence and ongoing trials concerning the effects of CHMs for the treatment of COVID-19. **Methods:** This is a narrative review of relevant studies. Searches were conducted to identify documents published till April 22, 2020. Electronic databases, evidence-based collections, websites of relevant organizations, and trial registries were consulted. **Results:** A total of 25 guidelines on the treatment of patients with COVID-19 were identified. Four guidelines provided recommendations on the use of CHMs; these guidelines were developed in China and South Korea and were based on the consensus of experts exclusively. The remaining 21 guidelines provided no guidance on CHMs. No finished RCTs of CHMs for the treatment of patients with COVID-19 was found. According to the evidence evaluated in this review, a Cochrane review of CHMs for severe acute respiratory syndrome and five uncontrolled observational studies of the effects of CHMs in patients with COVID-19, the effects of CHMs for COVID-19 are unknown. A total of 52 ongoing clinical trials of CHM interventions for the treatment of COVID-19 were found. These trials will be carried out mostly in China (n = 51). Forty (77%) of the ongoing trials will be randomized, whereas 12 (23%) have an unclear sequence generation procedure. Forty-seven trials (90%) will have a sample size <400 participants. **Conclusions:** To the authors' knowledge, only the Chinese and the South Korean guidelines recommend CHMs as a treatment option for patients with COVID-19. These guidelines base their recommendations on the consensus of experts. Clinical guidelines or health authorities from other countries do not provide advice on CHMs.

Due to the absence of RCT, there is currently no reliable evidence on the effects of any specific CHM intervention for the treatment of patients with COVID-19. A high number of clinical trials of different herbal products are being currently conducted in China. (Lopez-Alcalde, J., et al, 2020).

Coronavirus disease 2019(COVID-19) refers to the pneumonia caused by novel coronavirus(2019-nCoV) infection in 2019. It is highly infectious, with quick spreading and a wide range of impact. It has been broken out in many countries around the world and has become a public health emergency of international concern. Chinese medicine has a long history in treating plague, and viral disease is the clinical advantage in Chinese medicine. Under the premise that there is currently no specific drug treatment, Chinese medicine has achieved certain effects in the treatment of COVID-19, which has attracted much attention and has been upgraded to a national strategy. Regarding the treatment of COVID-19 with Chinese medicine, it is believed that in terms of the name of Chinese medicine, the modern connotation of "uniform of typhoid and febrile disease" should be re-recognized, and it is advisable to use drugs based on specific clinical prescriptions and indications. In terms of pathogenesis, the COVID-19 has the pathogenesis rules including from the mild to severe conditions, from the surface to the inside, from the excess syndrome to the deficiency syndrome. We should pay attention to the Taiyang syndrome damaged by wet disease in initial stage, Shaoyang syndrome complicated with Yangming syndrome in the middle stage, phlegm-heat obstructing lung in critical period, lung and spleen deficiency in the recovery stage. In terms of clinical treatment strategies, Dayuan Yin is recommended to induce sweat and disperse the stasis in early stage. Xiaochaihu Decoction and Maxing Shigan Decoction is used to relieve both exterior and interior symptoms in middle stage. In critical stage, Tingli Dazao Xiefei Decoction, Weijing Decoction, Xuanbai Chengqi Decoction, Xiaoxianxiong Decoction, and Sanzi Yangqin Decoction are considered to reduce phlegm and clear heat. We should pay attention to nourishing Qi and strengthening the spleen by Zhuye Shigao Decoction, Sha-shen Maidong Decoction, and LiuJunzi Decoction in the later recovery period. It shall be noted that, no matter in the

initial mild stage, the middle and critical stages, or in the later recovery stage, Chinese medicine plays an important role, including preventing mild to severe disease, shortening the fever time, improving cough symptoms, increasing blood oxygen saturation and reducing mortality. Many studies have shown that the classical herbal formulae can alleviate the cytokine storm, regulate the immune imbalance, and produce the potential effect of synergistic treatment for COVID-19 through multiple components, multiple targets, and multiple pathways. (Su, K. L. and X. J. Xiong, 2021).

Background: In January, national guidelines were developed and recommended for use throughout China to fight coronavirus disease 2019 (COVID-19). Chinese herbal medicine (CHM) was also included as part of the treatment plans at various stages of COVID-19. Methods: We conducted a pilot randomized, controlled trial in patients with severe COVID-19 in Wuhan, China. Eligible adult patients were randomly assigned in a 2:1 ratio to receive either CHM plus standard care or standard care alone for 7 days. The primary outcome was the change in the disease severity category of COVID-19 after treatment. Results: Between Jan 31, 2020, and Feb 19, 2020, 42 out of 100 screened patients were included in the trial: 28 in the CHM plus standard care group and 14 in the standard care alone group. Among 42 participants who were randomized (mean [SD] age 60.43 years [12.69 years]), 21 (21/42, 50%) were aged ≥ 65 years, 35 (35/42, 83%) were women, and 42 (42/42, 100%) had data available for the primary outcome. For the primary outcome, one patient from each group died during treatment; the odds of a shift toward death was lower in the CHM plus group than in the standard care alone group (common OR 0.59, 95% CI 0.148-2.352, $P = 0.454$). Three (two from the CHM plus group and one from the standard care alone group) patients progressed from severe to critical illness. After treatment, mild, moderate, and severe COVID-19 disease accounted for 17.86% (5/28) vs. 14.29% (2/28), 71.43% (20/28) vs. 64.29% (9/28), and 0% (0) vs. 7.14% (1/28) of the patients treated with CHM plus standard care vs. standard care alone. Conclusions: For the first time, the G-CHAMPS trial provided valuable information for the national guideline-based CHM treatment of hospitalized patients with severe COVID-19. The effects of CHM in COVID-19 may be clinically important and

warrant further consideration and studies. Clinical Trial Registration: <http://www.chictr.org.cn/index.aspx>. Uniqueidentifier: ChiCTR2000029418. (Ye, Y. A. and G. C. C. Group, 2020).

STUDY DESCRIPTION:

The study has retrospectively investigated outcome of patients with Covid-19 who have been tested positive for Covid-19 and immediately after that treated with a herbal-compound called Xagrotin. The outcome is compared to the outcome of patients in same situation who have treated with standard treatment for Covid-19, but not including Xagrotin. 361 patients included in the first group and 178 in the second group. We analyzed the effect of drug, and also investigated impact of different factors, for instance gender, age, duration of disease, smoking habits and concomitant diseases on the outcome. Adverse events were also registered.

Key word: Covid-19, Herbal Compound, Xagrotin

STUDY DESIGN

This is an interventional, multi-center, randomized study in adult patients with Covid-19 that was conducted for 5 months (June 2020 – December 2020). The present study was performed to treat the risks of coronavirus disease. This study consisted of two phases and in parallel. Informed consent was obtained from all patients. In this study, 539 adults with laboratory or clinically confirmed Covid-19 disease in an outpatient setting were enrolled and divided into two groups: the study group (n=361) treated with Xagrotin extract 2 grams three times a day, plus the standard of care for covid-19, and the control group (n=178) was treated with the standard of care for covid-19, respectively. Patients enrolled in the current study at approximately 20 cities.

Inclusion Criteria

All adult patients in an outpatient setting who were confirmed as coronavirus patients were eligible to be included in the study.

Exclusion Criteria

In this study, we excluded the patients with the following criteria; age under 18 years, patients with incomplete information regarding sex, age, duration of disease, any drug usage, symptoms, ...etc.

Safety endpoints

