During the onset of Covid-19 pandemic, the Xagrotin drug has been synthesized and made available continuedly to the indigenous people. Since the initial statistical outcomes showed the

satisfactory results; we have not stopped collecting new data. The new collected data and analysis confirms the previous results.

Randomization and blinding

Among over 11000 eligible Covid-19 patients who had taken Xagrotin for their Covid-19 infections, we randomly selected 361 patients to be included in the study group where 178 eligible Covid-19 patients were randomly recruited to the control group.

Populations and subgroups to be analyzed

-Populations

All randomized study subjects will be included in an “intention to treat” analysis. This will be seen as the primary population for the analysis.

-Analysis

This analysis evaluates the efficiency and safety of Xagrotin, a herbal combination drug, in treatment of patients with covid-19 compared to routine drugs used for coronavirus in hospitals. Statistical analysis was carried out by Statistical Package for the Social Sciences (SPSS, V.23). At first, the Kolmogorov–Smirnov test was used to analyze the distribution normality of data. Data with normal distribution were shown as mean \pm SD. An Independent t-test was used to perform mean comparisons for normally distributed data. Mann-Whitney and Kruskal-Wallis tests were used for the analysis of non-normal data. Correlations between variables were measured using Pearson correlation and Spearman rank correlation tests for normal and non-normal data, respectively, with a 95% confidence interval. Regression analysis was used to evaluate the effect of Xagrotin on the risk of mortality and hospitalization in Covid-19 patients.

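### Background Covid treatment, city and calendar time are in no stated analysis, although the groups were not formed by chance allocation and standard care is undefined

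*Protocol*

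**What the plan says.** **Comparison.** The protocol's Study Design section gives the study group Xagrotin "plus the standard of care for covid-19, and the control group (n=178) was treated with the standard of care for covid-19, respectively". The Study Description calls the controls "patients in same situation who have treated with standard treatment for Covid-19, but not including Xagrotin". The SAP, under Analysis, describes the comparison as "compared to routine drugs used for coronavirus in hospitals", whereas the protocol's setting is outpatient. Neither document lists the drugs in standard care.

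**Place and time.** Study Design states "Patients enrolled in the current study at approximately 20 cities", with conduct from June to December 2020.

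**Formation of groups.** The SAP (Randomization and blinding) samples 361 patients at random from more than 11000 who had already taken Xagrotin, and recruits 178 controls separately. The Study Description calls the investigation retrospective; Study Design calls it randomized.

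**Drug data.** The Exclusion Criteria remove "patients with incomplete information regarding sex, age, duration of disease, any drug usage, symptoms", among other items. Drug use should therefore be on file in some form for each included patient.

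**Analysis.** The factors named in the Study Description are the "impact of different factors, for instance gender, age, duration of disease, smoking habits and concomitant diseases on the outcome". The SAP gives an independent t-test, rank tests and correlations, and then: "Regression analysis was used to evaluate the effect of Xagrotin on the risk of mortality and hospitalization in Covid-19 patients". It names no covariate for that regression and mentions no regression for duration.

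**The concern.** An add-on comparison isolates the added product only if the rest of the treatment is alike in both groups. Random allocation would achieve that on average. Sampling at random from people who had already chosen or been given Xagrotin does not, because it makes the sample represent the takers and does nothing to make takers resemble controls.

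Covid drugs may have differed between cities and over the months of the study. The protocol itself gives one reason why co-prescribing might differ by group: its safety section says that Xagrotin may affect CYP3A4 and that combined use needs monitoring. The drug-related exclusions cover anticoagulants and certain CYP3A4 medicines, not Covid drugs.

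This is confounding by co-treatment and period. Adjusting for age, sex, smoking and concomitant disease removes it only so far as prescribing followed those factors. The Xagrotin estimate is at stake on both primary outcomes (mortality and duration) and on hospitalization.

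**Working it through.** **1. What the documents supply.** Group sizes are 361 and 178. There are no event rates, no SD for duration and no background-drug shares. The one planning figure, a sample size of 370, reproduces: 1.96² × 0.5 × 0.5 / 0.05² = 384.16, and 10000 × 384.16 / (9999 + 384.16) = 369.98. It is a precision formula for a single proportion, so it contributes no event rate or effect size. Everything below rests on assumed inputs, with a true Xagrotin effect of zero.

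**2. Apparent risk ratio for death.** Suppose a background drug cuts deaths by 30% and is used by shares p1 of the Xagrotin group and p2 of controls. Then

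RR = (1 − 0.3 × p1) / (1 − 0.3 × p2).

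| Use, Xagrotin v control | Calculation | Apparent RR |
|---|---|---|
| 60% v 20% | 0.82 / 0.94 | 0.87 |
| 20% v 60% | 0.94 / 0.82 | 1.15 |
| 50% v 30% | 0.85 / 0.91 | 0.93 |

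Other assumed drug effects (drug RR 0.8, 0.65, 0.5) give:

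| Use, Xagrotin v control | Apparent RR |
|---|---|
| 50% v 40% | 0.98, 0.96, 0.94 |
| 60% v 30% | 0.94, 0.88, 0.82 |
| 80% v 20% | 0.88, 0.77, 0.67 |

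**3. Could this produce a very small P on a binary outcome?** The standard-error factor is √(1/361 + 1/178) = 0.0916.

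- For 60% v 20% use and the 30% drug, control risks of 5% to 20% give z of about 0.3 to 0.7.
- The most extreme case examined is an untreated risk of 20%, a drug that halves it, and 80% v 20% use. Risks are 0.12 and 0.18; the pooled risk is (361 × 0.12 + 178 × 0.18) / 539 = 0.140; z = 0.06 / (√(0.140 × 0.860) × 0.0916) = 1.89.
- A two-sided P of 0.001 needs z = 3.29.
- The chance of P < 0.05 is 5% to 16% at 60% v 30% use, and 6% to 47% at 80% v 20%, over untreated risks of 2% to 20% and drug RRs of 0.5 to 0.8.

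**4. Duration.** Spurious gain = gap in use × days saved by the background drug. With an assumed SD of 5 days, the standard error is 5 × 0.0916 = 0.458. For a 40-point gap:

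| Drug shortens illness by | Spurious gain | z | p |
|---|---|---|---|
| 1 day | 0.4 day | 0.87 | 0.38 |
| 2 days | 0.8 day | 1.75 | 0.08 |
| 3 days | 1.2 days | 2.62 | 0.009 |

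Reaching P = 0.001 at this gap needs 3.29 × 0.458 / 0.4 = 3.8 days saved. For a 2-day drug and SD of 4 to 6 days, a 30-point gap gives a false gain of 0.6 day and P < 0.05 in 19% to 37% of studies. A 60-point gap gives 1.2 days and 59% to 91%. Duration is therefore more exposed than the binary outcomes.

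**The case against.** **No imbalance is shown.** This stands. A reader might infer that a difference in background drugs has in fact been credited to Xagrotin. The documents do not support that: they report no background-drug use by group, and the bias could favour either group.

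**The groups may have been concurrent.** The protocol gives one study window for all 539 patients, describes phases run in parallel, and places the controls in the same situation as the treated. That points towards overlapping periods and weakens any suggestion that controls came from different months. It does not establish balance by month or city.

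**Drug use may be in the model.** The factor list is given by way of example and the regression names no covariates, so deliberate omission is not proven. What stands is that no adjustment is specified, and that no adjusted analysis of any kind is stated for duration.

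**The data may not suffice.** A reader might take the exclusion rule to mean that Covid drugs are fully recorded. It requires only complete drug usage, possibly to apply the anticoagulant and CYP3A4 exclusions. Drug class and start dates may be missing, and no index date is defined for controls.

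**The study is finished.** The SAP gives completion as February 2021 and already reports results. Covariates would be chosen with results known. This stands and must be disclosed.

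**It is a consequence of non-random groups.** True, but correcting for the named patient factors alone could leave this part in place, so it needs its own terms in the model.

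**Conclusion.** The point holds in conditional form. The groups were not formed by chance allocation, standard care is undefined, its description differs between the documents, and drug use, city and calendar time are in no stated analysis. Any difference in background Covid drugs or period would therefore pass into the Xagrotin estimate, with unknown direction.

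Under the assumed inputs the bias is modest for modest imbalances (apparent RR 0.93 for 50% v 30% use of a drug that cuts deaths by 30%) and becomes large only when a strongly effective drug was very unevenly used (0.67 for 80% v 20% use of a drug that halves deaths).

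A reader might go further and conclude that co-treatment accounts for the SAP's report of P <0.001 for most results. On the binary outcomes the calculations do not support this, since even the most extreme case gives z = 1.89. This is a change that should be made; it does not by itself overturn the reported results.

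**What to change.** 1. Reconcile the descriptions of the comparator (outpatient standard of care, standard treatment without Xagrotin, routine hospital drugs) and list the background Covid drugs actually used.
2. Tabulate those drugs by group, city and month.
3. Replace the unadjusted duration test with a regression on treatment group, age, sex, smoking, concomitant diseases, Covid-drug class in use at or before the index date, calendar month, and city or region. Duration, though listed among the factors, is itself a primary outcome and is not a covariate here.
4. Use the same terms for mortality and hospitalization, through a single propensity score if events are few.
5. Define the index date for controls. Do not adjust for drugs started after it, since these may follow worsening or the treatment itself.
6. Report how many patients are lost in months or cities that lack one of the groups.
7. State that the re-analysis is post hoc. If drug class or dates were not recorded, say so and limit the conclusion to an association.

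The cost is SAP text, tables and additional models, largely on data that inclusion already required, though the necessary detail may be absent. Intervals will widen, possibly appreciably with many terms and only 178 controls, and some patients will drop out for lack of overlap.

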Treatment of Covid-19 With a Herbal Compound, Xagrotin

NCT05017493

ClinicalTrials.gov Submission Date 30- NOVEMBER -2021

Unique Protocol Identification Number: **02-032021-SULXAG/NO**

Protocol Version 1.4.2: 24- NOVEMBER-2021

Study Type: **Interventional**

Record Verification Date: **March, 2021**

Board Approval Number: **118/KRGJUL/CH/ADM/ 09**

Board Name: **Institutional Ethical Committee**

Board Affiliation: **Directorate of health of Sulaimani, Iraq -KRG**

Study start Date: July 1, 2020 [Actual]

Primary Completion Date: December 7, 2020 [Actual]

Study Completion Date: February 8, 2021 [Actual]

Sponsor: Biomad AS

Responsible Party: Sponsor

Collaborators: Directorate of health of Sulaimani, Iraq -KRG

Sample size calculation

The aim of this clinical trial was to evaluate the short-term effects of Xagrotin in improving Covid-19 symptoms in patients as well as reducing mortality in Covid-19 patients.

Out of the 11000 eligible patients, we selected 539 patients. The 539 patients were divided into two groups. The sample size is calculated by following formula:

Parameter	Value
Study population	10000
Confidence interval 95 % (Z)	1.96
Margin of Error (e)	0.05
Uncertainty sample ratio (P)	0.5
Sample ratio	0.05

$$\text{Sample size: } N \times \frac{\frac{Z^2 \times p \times (1-p)}{e^2}}{[N-1 + \frac{Z^2 \times p \times (1-p)}{e^2}]}$$
$$= (10000 \times (1.96^2) \times 0.5 \times (1-0.5)) / (10000 - 1) + (1.96^2) \times 0.5 \times (1-0.5) / (0.05^2)$$

Sample size= 370

To confirm the sufficient sample size of the study, we compared the results of the two groups. Comparison of the results of the two study groups showed that the statistical difference between the two groups was significant (< 0.001). The Pocock boundary and the O'Brien-Fleming boundary consider P-value= 0.02 as strength of evidence to stop a trial for benefit. However, the Haybittle-Peto boundary has shown that if data has a statistical difference at the level of P <0.001, it can be considered as evidence for stopping an early trial for benefit. Most of the results of our study had a P-value <0.001 that allowed us to stop sampling. On the other hand, our results showed a major therapeutic advancement. Given the high mortality rate of Covid-19 in the world, we ethically needed to stop random sampling in current clinical trial study and publish the results as soon as possible.

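### Xagrotin takers and controls are not shown to be aligned in calendar time within the study window, and no specified analysis accounts for period

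*Protocol*

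**What the plan says.** **Window.** The Protocol (Study Design) says the study was "conducted for 5 months (June 2020 – December 2020". The SAP's title block has "Study start Date: July 1, 2020 [Actual" and "Primary Completion Date: December 7, 2020 [Actual".

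**Design.** The Protocol's Study Description says "The study has retrospectively investigated outcome of patients with Covid-19". Its Study Design section says "This is an interventional, multi-center, randomized study in adult patients with Covid-19", and adds "This study consisted of two phases and in parallel" without explaining what the phases are or whether the phrase refers to the two treatment groups. The Study Description presents controls as being in a comparable situation, with no mention of calendar time.

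**How the groups were formed.** The SAP (Randomization and blinding) says "we randomly selected 361 patients to be included in the study group where 178 eligible Covid-19 patients were randomly recruited to the control group". The 361 came from more than 11000 people who had already used the product. No source, dates or matching rule is given for the 178. At the end of its sample size section, the SAP says that since the onset of the pandemic "the Xagrotin drug has been synthesized and made available continuedly to the indigenous people", and that data collection continued.

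**Analysis.** The SAP names the t-test, Mann-Whitney, Kruskal-Wallis, two correlation coefficients, and a regression for mortality and hospitalization whose covariates are not listed. The Protocol's Study Description gives, as examples, sex, age, disease duration, smoking and comorbidity as factors examined. No date or month appears in either place.

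**The concern.** Thirty-day mortality, days with symptoms and hospitalization can all plausibly vary over an epidemic with case load, bed access, testing and background care. Random allocation of patients as they present would spread takers and controls over the same weeks. Random sampling from two separately assembled sources does not: each sample inherits the calendar mix of its source.

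If that mix differs, the crude comparison contains a calendar difference that has nothing to do with the product. Adjusting for age, sex, comorbidity or city would not remove it, because it would arise within one city among otherwise similar patients. A small P-value, such as the SAP relies on to justify stopping, does not exclude it.

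**Working it through.** **1. The stated duration.** The Protocol's own figure is 5 months. Taking a month as 30.44 days:

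- SAP dates, 1 July to 7 December 2020: 30 + 31 + 30 + 31 + 30 + 7 = 159 days; 159 / 30.44 = 5.2 months. This reproduces the 5 months.
- Protocol months with both counted in full, 1 June to 31 December: 213 days; 213 / 30.44 = 7.0 months.
- Protocol months at their shortest, 30 June to 1 December: 154 days; 154 / 30.44 = 5.1 months.

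The Protocol's length therefore agrees with its own month names only in the extreme case, and any patient from June precedes the SAP's actual start.

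**2. What could align the groups in time.**

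| Possible safeguard | What the documents show |
|---|---|
| Random allocation | Called randomized, but the SAP describes sampling existing takers and separate recruitment of controls |
| One window for all 539 | Stated in the Protocol, with conflicting dates; no monthly mix by group |
| Matching or stratification on date | Not mentioned |
| Calendar term in an analysis | None named; the tests usable for duration are unadjusted, and the regression covariates are unlisted |

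**3. How large the bias could be.** No period-specific risk or monthly count is given, so all risks and shares here are assumptions. With no drug effect, low-period risk a, high-period risk b and low-period share s, a group's risk is s·a + (1 − s)·b.

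With a = 1% and b = 4%:

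| Low-period share, Xagrotin / control | Xagrotin risk | Control risk | Apparent risk ratio |
|---|---|---|---|
| 70% / 40% | 0.7×1 + 0.3×4 = 1.9% | 0.4×1 + 0.6×4 = 2.8% | 0.68 |
| 60% / 50% | 0.6×1 + 0.4×4 = 2.2% | 0.5×1 + 0.5×4 = 2.5% | 0.88 |
| 40% / 70% | 2.8% | 1.9% | 1.47 |

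**4. False positives at 361 v 178.** The calculation uses a two-sided 5% pooled z-test and a normal approximation, which is rough at low event counts. With d = p1 − p2, SE0 the pooled and SE1 the unpooled standard error, the rejection rate is Φ((−1.96·SE0 − d)/SE1) + 1 − Φ((1.96·SE0 − d)/SE1).

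Example: risks 5% v 10%, shares 70/30. The group risks are 6.5% and 8.5%, d = −0.020, SE0 = 0.0236, SE1 = 0.0246. The rate is Φ(−1.07) + 1 − Φ(2.69) = 0.143 + 0.004, about 15%.

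| Assumed risks, low v high | Risk ratio at 70/30 | False positives |
|---|---|---|
| 1% v 2% | 0.76 | 8% |
| 2% v 6% | 0.67 | 17% |
| 5% v 10% | 0.76 | 15% |
| 10% v 20% | 0.76 | 25% |

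With equal shares the ratio is 1.00 and the rate 5% in every row.

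**5. How fine an adjustment the data could carry.** At an assumed control mortality of 2.8%, 178 × 0.028 = 5.0 control deaths. Over 5.2 to 7.0 months that is 1.0 to 0.7 per month, too few for monthly strata.

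**The case against.** The Protocol gives one window for all 539 patients and describes the study as parallel. A reader might infer that the groups came from different calendar periods. The documents do not support that: the continuous supply described in the SAP concerns availability of the product, the Protocol's safety section says the product was offered alongside the study, and nothing says any of the 361 fell outside the window. What remains is that alignment within the window is undocumented.

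A reader might also infer that the analysis omitted month. That cannot be shown. The regression covariates are unnamed and the Protocol's factor list is only illustrative, so the accurate statement is that no calendar term is specified.

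The Protocol's background mentions dexamethasone and other repurposed drugs as under development, which might be read as evidence that care was changing. That sentence summarises a cited review and concerns severe disease, whereas this study enrolled outpatients. It should not be used as support.

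Nor do the illustrations show that timing produced the SAP's P-values. At 1.9% v 2.8%, expected deaths are 361 × 0.019 = 6.9 and 178 × 0.028 = 5.0. The pooled standard error is 0.0134, so z = 0.009 / 0.0134 = 0.67 and P is about 0.5, far from the P <0.001 that the SAP reports.

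Finally, because the SAP's dates fit 5 months, June may be a clerical slip, and calendar time is only one consequence of non-random allocation. Both points are fair. They limit the weight of the concern but do not answer it.

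**Conclusion.** The concern holds as a gap in documentation and analysis. Sampling existing takers and recruiting controls separately does not balance calendar time, no other stated feature does, and no specified analysis accounts for it. The study dates also conflict between the documents, and the Protocol's duration sits badly with its own months.

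Bias in mortality, duration and hospitalization is possible in either direction and is not demonstrated. Its size cannot be computed from the documents. The risk ratios of 0.68, 0.88 and 1.47 and the 8% to 25% false-positive rates rest wholly on assumed period risks and assumed mixes; with equal mixes the bias is nil. This is a worthwhile, inexpensive improvement within the larger problem of non-random allocation.

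**What to change.** 1. Reconcile the Protocol and SAP into one window, and state whether its end refers to the last diagnosis or the last 30-day assessment.
2. Restrict both groups to patients diagnosed within it, and give the source and dates of the controls.
3. Report patients per group per month of diagnosis. If the mixes agree, the table itself largely answers the concern.
4. Adjust each comparison for calendar period of diagnosis: by month for duration and, if event counts allow, for hospitalization. For mortality, use two or three blocks or a smooth or linear time term, with penalised or exact regression if events are few.
5. Periods with patients in only one group should not contribute. With a smooth or linear term, restrict to the overlapping period first, so that the model does not extrapolate.
6. List the regression covariates. Because results have already been seen, set block boundaries without reference to outcomes and label the analysis as added later.

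The cost is SAP wording and a small re-analysis. Some patients drop out and intervals widen, possibly noticeably for mortality; coarse blocks leave some residual confounding within them. Diagnosis dates must be retrievable. The Protocol's 10-day limit since diagnosis suggests they are, but the data items it names as required do not include them. The change addresses calendar time only and leaves the other consequences of non-random allocation in place.
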